3.4.1 Assessment for SARS-CoV-2 Infection

Study participants will have nasopharyngeal swab samples collected for SARS-CoV-2 testing at time points specified in the Schedule of Events (Part A [Table 9](#) and Part B [Table 10](#), [Table 11](#) and [Table 12](#), and Part C [Table 12](#)).

For Part A, Part B, and Part C of this study, a study illness visit or a consultation will be arranged within 24 hours or as soon as possible to collect a nasopharyngeal swab sample to ascertain the presence of SARS-CoV-2 via PCR if a participant experiences any of the following:

- Signs or symptoms of SARS-CoV-2 infection as defined by the CDC ([CDC 2020c](#))
- Exposure to an individual confirmed to be infected with SARS-CoV-2
- MAAE suggesting a SARS-CoV-2 infection

Additionally, clinical information will be carefully collected to evaluate the severity of the clinical case. All findings will be recorded in the eCRF.

If scheduled, a study site illness visit may include assessments such as medical history, physical examination, blood sampling for clinical laboratory testing, and nasopharyngeal swab sampling for viral PCR (including multiplex PCR for respiratory viruses including SARS-CoV-2) to evaluate the severity of the clinical case. Radiologic imaging studies may be conducted. Blood samples will be collected at all illness visits for potential future immunologic assessment of SARS-CoV-2 infection.

If participants are confirmed to have SARS-CoV-2 infection, the investigator will notify the participant’s primary care physician of the diagnosis. Additionally, a convalescent visit will be scheduled approximately 28 days after diagnosis. At this visit, a blood sample will be collected for potential future immunologic assessment of SARS-CoV-2 infection.

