2. All scheduled study visits should be completed within the respective visit windows. If the participant is not able to come on site for a study site visit as a result of the COVID-19 pandemic (self-quarantine or disruption of study site activities following business continuity plans and/or local government mandates for “stay at home” or “shelter in place”), a safety call to the participant should be made in place of the study site visit. The safety call should encompass all scheduled visit assessments that can be completed remotely, such as assessment for adverse events and concomitant medications (eg, as defined in scheduled safety telephone calls). Home visits will be permitted for all non-dosing visits except for Screening if a participant cannot come to the study site as a result of

the COVID-19 pandemic. Home visits must be permitted by the site IRB and the participant via informed consent and have prior approval from the Sponsor (or its designee).

3. If the visit for the second dose (Day 29) is disrupted and cannot be completed at Day 29 +7 days as a result of the COVID-19 pandemic (self-quarantine or disruption of clinical site activities following business continuity plans and/or local government mandates for “stay at home” or “shelter in place”), the window may be extended to Day 29 + 21 days. When the extended window is used, the remaining study visits should be rescheduled to follow the inter-visit interval from the actual date of the second dose.
4. Safety follow-up via eDiary questionnaire will be performed every 4 weeks starting at Day 71 to Day 183 and again starting at Day 223 to Day 363. These study days are relative to Day 1 vaccine administration and are not affected by the timing of the second vaccine administration.
5. Safety follow-up via a safety telephone call will be performed every 4 weeks starting at Day 85 to Day 197 and again starting at Day 237 to Day 377. There is potential overlap of the Day 197 safety telephone call and Visit 8 due to their respective visit windows. As such, the safety telephone call on Day 197 only needs to be performed if the participant is scheduled to complete Visit 8 after Day 200.
6. Safety laboratory tests include the following: CBC with differential, AST, ALT, total and direct bilirubin, ALP, BUN/creatinine, PT/PTT. Safety laboratory tests are to be repeated at Day 29 and Day 57 **only for Cohort 2 (≥ 55 years old)**.

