3. Physical examination: A symptom-directed physical examination, including height and weight, will be performed at OL-Day 1, OL-Day 29, and OL-Day 57. Symptom-directed physical examinations may be performed at other time points at the discretion of the investigator. Any clinically significant finding identified during a study visit should be reported as an MAAE. Vital signs are to be collected pre- and post-dosing on days of injection (Day 1 and Day 29). When applicable, vital sign measurements should be performed before blood collection. Participants who are febrile (body temperature $\geq 38.0^{\circ}\text{C}/100.4^{\circ}\text{F}$) before injection on OL-Day 1 or OL-Day 29 must be rescheduled within the relevant window period to receive the injection. Afebrile participants with minor illnesses can be administered investigational product at the discretion of the investigator.
4. Sample must be collected prior to dosing on days of injection.
5. The nasopharyngeal swab sample, collected prior to vaccination on days of injection, will be used to ascertain the presence of SARS-CoV-2 via PCR.
6. Diary entries will be recorded by the participant starting approximately 30 minutes after injection while at the study site with instruction provided by study staff. Study participants will continue to record in the eDiary each day after they leave the study site, preferably in the evening and at the same time each day, on the day of injection and for 6 days following injection. Any solicited AR that is ongoing beyond Day 7 will be reported in the eDiary until resolution. Adverse reactions recorded in eDiaries beyond Day 7 should be reviewed either during the next telephone call or at the next study site visit.

7. Trained site personnel will call all participants to collect information relating to any AEs, MAAEs, SAEs, AEs leading to study withdrawal, information on concomitant medications associated with those events, and any non-study vaccinations. In addition, study personnel will collect information on known participant exposure to someone with known COVID-19 or SARS-CoV-2 infection and on participant experience of COVID-19 symptoms. Sites will collect this information for diary days only if diary responses indicate the need for follow-up via telephone.

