Consists of all periods that begin 28 days after the last injection in Part A (ie, the day of last injection in Part A + 28 days, regardless of number of injections received) and continue until the earliest date of first injection in Part B, and all periods that begin 28 days after the last injection in Part B (ie, the day of last injection in Part B + 28 days, regardless of number of injections received) and continue until the earliest date of (study completion, discontinuation from the study, or death).

- Day 1 to End of Study: Begins at the first injection on Day 1 and continues through the earliest date of (study completion, discontinuation from the study, or death).
- 28 days after any vaccination stage: This stage starts at the day of each vaccination and continue through the earliest date of (the day of each vaccination and 27 subsequent days, next vaccination (if applicable)).

Unscheduled visits: Unscheduled visit measurements will be included in analysis as follows:

- In scheduled visit windows per specified visit windowing rules.
- In the derivation of baseline/last on-treatment measurements.
- In the derivation of maximum/minimum on-treatment values and maximum/minimum change from baseline values for safety analyses.
- In individual subject data listings as appropriate.

Visit windowing rules: The analysis visit windows for protocol-defined visits are provided in [Appendix B](#).

Incomplete/missing data:

- Imputation rules for missing prior/concomitant medications, non-study vaccinations and procedures are provided in [Appendix C](#).
- Imputation rules for missing AE dates are provided in [Appendix D](#).
- For laboratory assessments, if majority of results are indefinite, imputation of these values will be considered. If the laboratory results are reported as below the LLOQ (eg, <0.1), the numeric values will be imputed by $0.5 \times \text{LLOQ}$ in the summary. If the laboratory results are reported as greater than the ULOQ (eg, >3000), the numeric values will be imputed by ULOQ in the summary.

- Other incomplete/missing data will not be imputed, unless specified otherwise.

The following vaccination **groups** will be used for summary purposes:

- Part A, Blinded Phase:
 - mRNA-1273 50 µg
 - mRNA-1273 100 µg
 - mRNA-1273 Total
 - Placebo
- Part B, Open-Label Phase:
 - mRNA-1273 50 µg - Booster
 - mRNA-1273 100 µg - Booster
 - mRNA-1273 - Booster Total
 - Placebo - mRNA-1273

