9.2. Appendix B Analysis Visit Windows for Safety and Immunogenicity Analysis

Safety and Immunogenicity Analysis will be summarized using the following analysis visit window for post injection assessments:

Step 1: If the safety and immunogenicity assessments are collected at scheduled visit, i.e. nominal scheduled visit, the data collected at scheduled visit will be used.

Step 2: If the safety and immunogenicity assessments are not collected at the scheduled visit, assessments collected at unscheduled visit will be used using the analysis visit windows described in [Table 4](#) below.

If a subject has multiple assessments within the same analysis visit, the following rule will be used:

- If multiple assessments occur within a given analysis visit, the assessment closest to the target study day will be used.
- If there are 2 or more assessments equal distance to the target study day, the last assessment will be used.

Table 4 Visit Window

Visit	Target Study Day	Visit Window in Study Day
Labs		
Day 29 (Month 1)	29 (Date of Second Injection)	[2, 43]
Day 57 (Month 2)	57	≥44 and prior to Participant Decision Visit

Nasal Swabs for SARS-CoV-2		
Baseline	1 (Date of First Injection)	≤ 1
Day 29 (Month 1)	29 (Date of Second Injection)	[2, 43]
Day 57 (Month 2)	57	[44, 70]
Day 71 or Beyond	71	≥ 71 and prior to Participant Decision Visit
Baseline (OL-Day 1)	1 (Date of First Injection on OL-Day 1) relative to OL-Day 1	≤ 1 and VISIT is OL-Day 1
OL-Day 29	29 (Date of Second Injection in Part B) relative to OL-Day 1	[2, 43]
OL-Day 57	57 relative to OL-Day 1	[44, 70]
OL-Day 71 or Beyond	71 relative to OL-Day 1	≥ 71
Vital Signs		
Day 8	8	[2, 11]
Day 15	15	[12, 22]
Day 29 (Month 1)	29 (Date of Second Injection)	[23, 32]
Day 36	36	[33, 39]
Day 43	43	[40, 50]
Day 57 (Month 2)	57	[51, 133]
Day 209 (Month 7)	209	[134, 301]
Day 394 (Month 13)	394	≥ 302 and prior to Participant Decision Visit
Baseline (OL-Day 1)	1 (Date of First Injection on OL-Day 1) relative to OL-Day 1	≤ 1 and VISIT is OL-Day 1
OL-Day 29	29 (Date of Second Injection in Part B) relative to OL-Day 1	[2, 43]
OL-Day 57 for subjects receiving 2 doses in Part B	57 relative to OL-Day 1	[44, 133]
OL-Day 209 for subjects receiving 2 doses in Part B	209 relative to OL-Day 1	≥ 134
OL-Day 57 for subjects receiving 1 dose in Part B	57 relative to OL-Day 1	[44, 119]

OL-Day 181 for subjects receiving 1 dose in Part B	181 relative to OL-Day 1	≥ 120
Immunogenicity		
Baseline	1 (Date of First Injection)	≤ 1

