Day 15	15	[2, 22]
Day 29 (Month 1)	29 (Date of Second Injection)	[23, 36]
Day 43	43	[37, 50]
Day 57 (Month 2)	57	[51, 133]
Day 209 (Month 7)	209	[134, 301]
Day 394 (Month 13)	394	≥ 302 and prior to Participant Decision Visit
Baseline (OL-Day 1)	1 (Date of First Injection on OL-Day 1) relative to OL-Day 1	≤ 1 and VISIT is OL-Day 1
OL-Day 8	8 relative to OL-Day 1	[2, 11]
OL-Day 15	15 relative to OL-Day 1	[12, 22]
OL-Day 29 (Month 1)	29 (Date of Second Injection) relative to OL-Day 1	[23, 43]
OL-Day 57 for subjects receiving 2 doses in Part B	57 relative to OL-Day 1	[44, 133]
OL-Day 209 for subjects receiving 2 doses in Part B	209 relative to OL-Day 1	≥ 134
OL-Day 57 for subjects receiving 1 dose in Part B	57 relative to OL-Day 1	[44, 119]
OL-Day 181 for subjects receiving 1 dose in Part B	181 relative to OL-Day 1	≥ 120

9.3. Appendix C Imputation Rules for Missing Prior/Concomitant Medications and Non-Study Vaccinations

Imputation rules for missing or partial medication start/stop dates are defined below:

1. Missing or partial medication start date:
 - If only DAY is missing, use the first day of the month, unless:
 - The CM end date is after the date of first injection or is missing AND the start month and year of the CM coincide with the start month and year of the first injection. In this case, use the date of first injection
 - If DAY and Month are both missing, use the first day of the year, unless:
 - The CM end date is after the date of first injection or is missing AND the start year of the CM coincide with the start year of the first injection. In this case, use the date of first injection
 - If DAY, Month and Year are all missing, the date will not be imputed, but the medication will be treated as though it began prior to the first injection for purposes of determining if status as prior or concomitant.
2. Missing or partial medication stop date:
 - If only DAY is missing, use the earliest date of (last day of the month, study completion, discontinuation from the study, or death).
 - If DAY and Month are both missing, use the earliest date of (last day of the year, study completion, discontinuation from the study, or death).
 - If DAY, Month and Year are all missing, the date will not be imputed, but the medication will be flagged as a continuing medication.

In summary, the prior, concomitant or post categorization of a medication is described in [Table 5](#) below.

Table 5 Prior, Concomitant, and Post Categorization of a Medication

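### When the scheduled sample is missing, the SAP's visit windows can report an unscheduled sample taken after dose 2 as the pre-dose-2 time point (OL-Day 29 in placebo crossovers, Day 29 in Part A)

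*SAP*

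**What the plan says.** SAP Appendix B (section 9.2) assigns assessments to time points in two steps. Step 1 uses the sample collected at the nominal scheduled visit. Step 2 applies when that sample is absent: "If the safety and immunogenicity assessments are not collected at the scheduled visit, assessments collected at unscheduled visit will be used", placed by the windows in Table 4. SAP section 6.1 confirms that unscheduled measurements enter the analysis: "In scheduled visit windows per specified visit windowing rules".

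Inside a window the choice depends on distance alone: "If multiple assessments occur within a given analysis visit, the assessment closest to the target study day will be used". If two samples are equally distant, the later one is taken.

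In the immunogenicity block of Table 4, Part A Day 29 has the window [23, 36]. OL-Day 29 has [23, 43], with the target given as "29 (Date of Second Injection) relative to OL-Day 1". Neither row carries a pre-dose condition.

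The protocol does. Its schedules of events (Table 9 for Part A, Table 11 for two-dose participants in Part B) state: "Sample must be collected prior to dosing on days of injection".

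**The concern.** In a two-dose series, the Day 29 and OL-Day 29 samples measure the response to one dose. That reading holds only if the blood precedes the second injection. Table 4 names the second injection as the target and then lets the window run past it. A sample drawn after dose 2 could therefore enter the geometric mean, the fold-rise and the seroresponse rate for the dose-1 time point. If antibody rises after dose 2, the error overstates the one-dose response. Placebo crossovers are the only Part B group with a second injection, so the issue in Part B is confined to them.

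**Working it through.** **Inputs.** Target days and windows come from SAP Table 4, immunogenicity block. The pre-dose requirement comes from Protocol Tables 9 and 11. Dose 2 is planned on Day 29 or OL-Day 29 with an allowance of +7 days (same tables). In Part A the allowance may be extended to +21 days for pandemic disruption (Table 9, footnote 3).

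**Step 1: reproduce the windows.** Take the upper limit as the midpoint of adjacent targets, rounded down.

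- Part A, targets 15, 29, 43, 57, 209, 394: (15+29)/2 = 22; (29+43)/2 = 36; (43+57)/2 = 50; (57+209)/2 = 133; (209+394)/2 = 301.5, so 301. Stated: 22, 36, 50, 133, 301.
- Part B, targets 8, 15, 29, 57, then 209 (two doses) or 181 (one dose): 11.5, so 11; 22; 43; then 133 or 119. Stated: 11, 22, 43, then 133 or 119.

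Every bounded limit agrees, so the windows are plain midpoints and the injection plays no part in them.

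**Step 2: count post-dose days in the pre-dose windows.** Post-dose days = upper limit − day of dose 2, with a floor of zero.

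| Dose 2 on day | Part A Day 29, [23, 36], 14 days | OL-Day 29, [23, 43], 21 days |
|---|---|---|
| 29 | 36 − 29 = 7 | 43 − 29 = 14 |
| 32 | 36 − 32 = 4 | 43 − 32 = 11 |
| 36 | 0 | 43 − 36 = 7 |

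With dose 2 on the planned day, half of the Part A window (7 of 14 days) and two thirds of the Part B window (14 of 21) lie after dosing.

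**Step 3: does another rule remove such a sample?** The tie-break does not. With dose 2 on day 29, no nominal sample, and unscheduled samples on days 27 and 31, both are 2 days from target and the later, post-dose sample is used. The Per-Protocol Sets (SAP section 5.6) select participants and do not screen individual samples. SAP section 6.1 does compare dates and times with each injection when it derives study day relative to the most recent injection, but Table 4 does not use that variable.

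**Step 4: effect of one misplaced sample.** The SAP's geometric mean averages logs, so one value of n that is too high by a factor R multiplies the mean by R^(1/n). For illustration, assume n = 100 (the planned placebo number per age cohort, all crossing over and evaluable) and R = 4 (the standard seroresponse fold). Then 4^(1/100) = 1.014, or 1.4% per affected participant. A smaller n raises this.

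**Step 5: late dose 2 in Part A.** The latest permitted dose 2 is Day 29 + 21 = Day 50. All 14 days of the Day 43 window [37, 50] then fall on or before dose 2, and days 51 to 56 of the Day 57 window are only 1 to 6 days after it. This concerns unscheduled samples only. Under Table 9, footnote 3, "the remaining study visits should be rescheduled to follow the inter-visit interval from the actual date of the second dose", and those rescheduled visits stay nominal under Step 1.

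**The case against.** The strongest reply is that the route is narrow and much of the ground is finished. Blood and injection belong to the same visit, so dose 2 must have been given without a usable nominal sample, and an unscheduled immunogenicity sample must exist in the following days. SAP section 1 says that the Day 57 report and the end-of-Part-A addendum are final and that nothing changes for Part A. The study tests no hypothesis. The booster comparison added in this SAP version (OL-Day 29 against Day 57, section 6.4.2) is untouched by the OL-Day 29 gap, because single-booster participants have no second Part B injection. All of this stands. It limits the size of the problem but supplies no rule that would keep a post-dose sample out.

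A reader might infer three larger problems that the documents do not support.

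- **Post-booster samples inflating Month 7.** The Day 394 row stops at the Participant Decision Visit ("302 and prior to Participant Decision Visit"), while the Day 57 and Day 209 rows do not. But a participant completes Part A on starting Part B (Protocol section 3.1.1), the parts are analysed separately (SAP section 6.4), and Part B rows already cover every post-booster day. Entering Part B before Day 209 does remove that nominal visit, so Table 4 should be explicit. Calendar dates cannot show wide exposure, because no Part B visit dates are given.
- **A late dose 2 corrupting Days 43 and 57 generally.** Scheduled visits are safe under Step 1, and SAP section 6.4.2 allows an optional sensitivity analysis for the extended window.
- **Infection samples filling vaccine time points.** The protocol says "Blood samples will be collected at all illness visits for potential future immunologic assessment". Nothing shows that this blood enters the immunogenicity data, which Protocol section 3.4.5 ties to the schedules of events. Nor would a window crossing an injection be the cause.

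**Conclusion.** The gap is real and minor. As written, Step 2 with Table 4 can place a sample taken up to 14 days after dose 2 at OL-Day 29 in placebo crossovers, or up to 7 days after dose 2 at Part A Day 29. Both figures assume dose 2 on the planned day; a later dose 2 shortens them. The direction of bias assumes that antibody rises after dose 2. A sample drawn in the first days after the injection may differ little.

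The number of participants affected is not in the documents and is probably small, since a missing nominal sample and an available unscheduled one must coincide. With the Part A reports final, the consequence falls mainly on the remaining Part B analysis. The missing Decision Visit stop on Days 57 and 209 and the unshifted Day 43 and Day 57 windows are matters of tidying and do not show that reported results are wrong.

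**What to change.** **Main change.** In Table 4, for participants who receive a second injection, end the OL-Day 29 immunogenicity window at the date and time of that injection. Apply the same cut to Part A Day 29 in any re-run. The date-and-time comparison in SAP section 6.1 can be reused, including its convention that a same-day assessment without a time counts as after the injection. Step 1 still protects nominal samples. Single-booster participants keep [23, 43].

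**Low-cost tidying.**

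1. Add to the Part A Day 57 and Day 209 rows the Participant Decision Visit stop that the Day 394 row already has.
2. For participants who received dose 2, place unscheduled Day 43 and Day 57 samples by days since the actual dose 2. Keeping the present spacing from a Day 29 dose gives 37 − 29 = 8 to 50 − 29 = 21 days for Day 43, and from 51 − 29 = 22 days for Day 57. Stop the Day 57 window at study day 133 so that it does not overlap Day 209.
3. Keep the study-day windows for participants without dose 2. At the 05 November 2020 cut these were 600 − (195 + 198 + 194) = 13.

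**Cost.** A few lines of SAP wording and derivation code. A few more time points become missing, because an unscheduled sample shortly after dose 2 would no longer fill one. Nominal samples are unchanged. A Part A re-run could differ slightly from the finalized reports, and any difference should be explained there.

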Part A, Blinded Phase of the study comprises up to 10 scheduled study site visits: Screening, Day 1, Day 8, Day 15, Day 29 (Month 1), Day 36, Day 43, Day 57 (Month 2), Day 209 (Month 7), and Day 394 (Month 13) or initiation of Part B, whichever is earlier. There are also scheduled participant contacts approximately every 2 weeks after Day 57 to collect MAAEs, AEs leading to withdrawal, SAEs, concomitant medications associated with these events, receipt of non-study vaccinations, exposure to someone with known COVID19 or SARS-CoV-2 infection, and participant experience of COVID-19 symptoms (Table 9). Every 4 weeks from Day 71 through Day 183 and from Day 223 through Day 363, each participant will complete a questionnaire in an electronic diary (eDiary) that will be reviewed by study site personnel. Safety telephone calls will occur every 4 weeks from Day 85 through Day 197 and from Day 237 through Day 377. The study duration will be approximately 14 months for each participant: a screening period of up to 1 month

and a study period of 13 months that includes the first dose of vaccine on Day 1 and the second dose on Day 29. The participant's final visit will be on Day 394 (Month 13), 12 months after the second dose of vaccine on Day 29 (Month 1), or at the initiation of Part B, whichever is earlier.

To test for the presence of SARS-CoV-2, nasopharyngeal swab samples will be collected at Day 1, Day 29, and Day 57. During the course of the study, participants meeting pre-specified disease criteria that suggest possible SARS-CoV-2 infection will be asked to contact the study site to arrange for a prompt, thorough, and careful assessment ([Section 3.4.1](#)).

Each participant will receive 2 injections of mRNA-1273 or placebo by 0.5 mL IM injection on Day 1 and Day 29. Vaccine accountability, dose preparation, and vaccine administration will be performed by unblinded pharmacy personnel who will not participate in any other aspects of the study during Part A, the Blinded Phase. The remainder of the study staff, all participants, and Sponsor personnel (or its designees) will remain blinded to dosing assignment ([Section 3.3.5](#)).

All participants will be followed for safety and reactogenicity and provide pre- and post-injection blood specimens for immunogenicity through 12 months after the last dose of investigational product. [Section 4.7](#) describes the planned study analyses.

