6.5.2. Nasopharyngeal Swab Assessments

Nasopharyngeal swab samples will be collected for SARS-CoV-2 testing. The number and percentage of subjects with detected and not detected will be summarized at each visit by age cohort and vaccination group as defined in [Section 6.1](#) for Part A and Part B separately.

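### The closest-to-target rule keeps only the earliest swab in the open-ended 'Day 71 or Beyond' window, so a later positive can be tabulated as not detected

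*SAP*

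**What the plan says.** Protocol 3.1.1 schedules Part A swabs on three days: "nasopharyngeal swab samples will be collected at Day 1, Day 29, and Day 57". Protocol Tables 11 and 12 schedule none after OL-Day 57 in Parts B and C. Later swabs come from Protocol 3.4.1: after symptoms, a known exposure or a suggestive medically attended event, "a study illness visit or a consultation will be arranged within 24 hours or as soon as possible to collect a nasopharyngeal swab sample". No limit on the number is given.

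SAP (Parts A/B) 6.1 places unscheduled results in the analysis windows of Appendix B. For swabs, the last Part A window in Table 4 has target day 71 and range "≥ 71 and prior to Participant Decision Visit". The last Part B window has target "71 relative to OL-Day 1" and range 71 or later with no upper limit. Table 1 of the Part C SAP has the same open-ended window.

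Both appendices then reduce several results in one window to a single result: "If multiple assessments occur within a given analysis visit, the assessment closest to the target study day will be used". For ties, "If there are 2 or more assessments equal distance to the target study day, the last assessment will be used". Section 6.5.2 of the Parts A/B SAP uses the result as follows: "The number and percentage of subjects with detected and not detected will be summarized at each visit by age cohort and vaccination group". Section 6.5.2 of the Part C SAP does the same by vaccination group. Neither section has an any-positive rule or exempts swabs from the windowing rule.

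**The concern.** A closest-to-target rule suits a titre or a vital sign measured around a planned day. The last swab window is different. It has no planned swab, its target is its first day, and its label covers the whole later period. A reader will take the row as the share of participants with virus detected at any time from Day 71. What it reports is the result of the first swab in that period.

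A negative swab after an exposure, followed months later by a positive swab at an illness visit, is an ordinary sequence under Protocol 3.4.1. The convalescent visit in that section calls for blood and does not mention a swab. The negative-then-positive order, which the rule loses, may therefore be at least as common as the reverse. The same report could then show a participant as infected in the adverse event output and as not detected in the swab table.

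**Working it through.** **Which swab the rule keeps.** The plan states no figure to reproduce here, so the check is of the rule itself. For a swab on day d ≥ 71, the distance from target is |d − 71| = d − 71, which rises with every later day. The smallest distance always belongs to the earliest swab. Applying the rule to every pair of distinct days from 71 to 394 confirmed this without exception. Swabs on the same day tie, and the last is kept.

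| Swabs in the window | Distances | Kept | Tabulated | Ever detected |
|---|---|---|---|---|
| Negative Day 80, positive Day 150 | 9 and 79 | Day 80 | not detected | yes |
| Negative OL-Day 75, positive OL-Day 120 | 4 and 49 | OL-Day 75 | not detected | yes |
| Positive Day 100, negative Day 180 | 29 and 109 | Day 100 | detected | yes |

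Step 1 of Appendix B, which prefers the scheduled visit, has nothing to select in this window. The provision in SAP 6.1 for maximum and minimum on-treatment values concerns values in safety analyses and supplies no any-positive rule for a swab.

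**Direction.** If the first swab is positive, the participant is ever-positive, but the converse fails. Compared with ever detected in the window, the tabulated count can only be equal or lower.

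**Size with a fixed number of late swabs (assumption).** Let each of k swabs be positive independently with probability q. The share of ever-positive participants shown as not detected is 1 − q / [1 − (1 − q)^k]. For k = 2 and q = 0.10 this is 1 − 0.10/0.19 = 0.47. Over q from 0.05 to 0.20:

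- 1 swab: 0%
- 2 swabs: 44% to 49%
- 3 swabs: 59% to 65%
- 4 swabs: 66% to 73%

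**Size across all participants (assumption).** Let the number of late swabs be Poisson with mean m. Then P(ever positive) = 1 − exp(−mq), P(first swab positive) = q[1 − exp(−m)], and the share lost is one minus the second over the first. At q = 0.10:

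| m | Ever positive | Tabulated as detected | Share lost |
|---|---|---|---|
| 0.25 | 2.47% | 2.21% | 10% |
| 0.5 | 4.88% | 3.93% | 19% |
| 1 | 9.52% | 6.32% | 34% |
| 2 | 18.13% | 8.65% | 52% |

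Over q from 0.05 to 0.20 the range runs from 9% (m = 0.25, q = 0.20) to 55% (m = 2, q = 0.05).

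**In participants.** At m = 0.25 and q = 0.10 the gap is 0.26 percentage points, about 0.5 of a participant in a group of 200. At m = 1 and q = 0.10 it is 3.2 points, about 0.6 of a participant in a Part C arm of 20.

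**The case against.** The strongest reply is that the table is descriptive, sits under exploratory analysis, and is not where the plan relies on infections being found. Protocol 3.4.1 has every confirmed infection, other than an asymptomatic one diagnosed at Day 1, recorded as a medically attended adverse event. Both SAPs tabulate medically attended treatment-emergent events by group (6.3.1.2) and give listings for infected participants (6.5.3). No visible endpoint uses the late swab window. The SAP's per-protocol sets for Parts A and B look at infection at baseline or OL-Day 1, and the Part C set has no infection criterion. All of this stands, and it makes the point minor. It does not make the row correct.

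A reader might infer more than the documents support:

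- **That the scheduled rows are wrong too.** Suppose an illness swab is positive on Day 12 and the scheduled Day 29 swab is negative. Step 1 then reports the Day 29 result in the Day 29 row. For a table of status by visit that is legitimate. Only the open-ended window lacks a scheduled swab.
- **That the loss differs by group and biases comparisons.** Nothing in the documents shows that swab frequency differs by group. The Part B and Part C summary groups all consist of people given open-label vaccine.
- **That this is the plan's only tabulation of infection.** The adverse event tables and listings show otherwise. The exploratory sections are blacked out, so other tabulations cannot be ruled out.
- **That about half of late infections vanish.** That holds only for participants with two or more late swabs under the assumptions above.

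**Conclusion.** The point holds as a defect in one row of one exploratory table, in both SAPs. The mechanism is certain from the text: the rule keeps the first swab on or after Day 71 (the last of several on that same day), so a later positive is tabulated as not detected. The direction is also certain, since the row can only understate the percentage ever detected in the window.

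The size is not known. The documents give neither swab counts nor positivity. The 9% to 55% range rests on assumed Poisson means of 0.25 to 2, positivity of 5% to 20%, and independence between swabs. With one late swab per participant nothing is lost. In absolute terms the loss can be under one participant per group at the lower swab rates shown. The conclusion carries no consequence for the visible endpoints or for the SAP's per-protocol sets. Severity is minor.

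**What to change.** Add one sentence to Appendix B of each SAP. For the nasal swab window Day 71 or Beyond / OL-Day 71 or Beyond only, classify a participant as detected if any swab in the window is positive, and as not detected only if at least one swab was taken and all are negative. Participants without a swab in the window stay out of both counts. Leave Step 1 and the scheduled Day 29 and Day 57 rows as they are.

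Apply this to Parts B and C. SAP (Parts A/B) Section 1 says the Part A Day 57 report and the end-of-Part-A addendum are finalized, so for Part A offer a supplementary table rather than reopening those outputs.

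The cost is one sentence per SAP, a small programming change and, for Part A, one extra table. No new data are needed.
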